6.3 Screening Assessments

The baseline assessments will be the last assessment performed before the injection of Flortaucipir F 18. The screening assessments includes the assessment performed during screening period and during the Florbetapir F 18 imaging visit.

The following screening and baseline assessments will be conducted prior to the injection of Flortaucipir F 18 :

- Informed consent;
- Eligibility criteria;
- Demographics (age, birth gender, education, race, ethnicity);
- Height will be collected as part of the ¹⁸F-AV-1451 imaging visit;
- Weight will be collected at both imaging visits prior to injection;
- Medical history, concomitant medications;
- Disease history;
- ECG will be performed to assess the subject's cardiac status if not performed within the last 12 months of enrollment;
- Cognitive status interview, including MMSE;
- MRI of the brain will be performed if not performed within one year of enrollment;

- Serum pregnancy test (women of childbearing potential);
- Urine pregnancy test prior to Flortaucipir F 18 injection;
- Vital signs (pulse rate, respiratory rate, supine blood pressure) immediately prior to Flortaucipir F 18 injection; Prior to the administration of Flortaucipir F 18 injection, and after the completion of Flortaucipir F 18 imaging, prior Flortaucipir F 18 to discharge.
- Flortaucipir F 18 PET dose administration;
- Flortaucipir F 18 PET scan;
- Follow-up call to confirm subject well-being and to collect any new adverse events.

Medical history will be coded using Medical Dictionary for Regulatory Activities (MedDRA) v 21.1 or higher to the preferred term (PT) and system organ class (SOC). Prior and concomitant medications will be coded using World Health Organization (WHO) Drug Dictionary version WHODrugDDEB2201809.

Weight will be displayed in kilograms (kg), height will be displayed in centimeters (cm). Weights and heights recorded in alternate units will be converted to the units being displayed using standard conversion formulas. Body Mass Index (BMI) will be calculated as:

- $BMI \text{ (kg/m}^2\text{)} = \text{Weight (kg)}/\text{Height (m)}^2$

Each subject's age (years) will be calculated as the difference of the year of his/her informed consent date and the year of his/her birth.

The MMSE (Folstein et al., 1975) is a brief instrument used to assess cognitive function in elderly subjects. The instrument is divided into two sections:

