7 STATISTICAL METHODS

7.1 General Methodology

All statistical analyses will be performed using SAS® version 9.3 or higher.

The study data collected under companion protocol such as but not limited to subjects' demographic and baseline characteristics, history taking, neurological and behavioral evaluations, and MRI will be transferred to Avid for analysis purposes. Amyloid scans used for review of enrollment criteria will also be transferred to Avid if applicable.

All values will be summarized as a single group, "Frontotemporal Dementia". Data will be summarized using descriptive statistics (number of subjects [N], mean, standard deviation [SD], quartiles, median, minimum, and maximum) for continuous variables and using frequency counts and percentage for discrete variables.

For the purpose of display, the summary results will be rounded as follows:

- Min and Max: same number of decimal places as the raw data.
- Mean and Median: one more decimal place than the raw data.
- 25th and 75th Percentile: one more decimal place than the raw data.

- SD: two more decimal places than the raw data.
- Percentages will be displayed with one decimal precision. A zero count will not have the associated percentage presented on the table.

For categorical variables with missing values, a category documenting the frequency of missing values will be displayed in the summary tables.

Subject listings of all data from the eCRF as well as any derived variables will be presented.

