7.8 Examination of Subgroups

No subgroup analysis will be performed.

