8.6 Disease History

Diagnosis of FTD will be summarize according to symptomatic clinical syndrome associated with expected FTD pathology by frequency counts and percentage. A listing related to diagnosis of FTD will be provided.

Disease history will be summarized using descriptive statistics for the subjects in Safety Population, and will include:

- Number of months since symptom onset
- Number of months since diagnosis

For subjects with dates of diagnosis or symptom onset is available, months will be calculated as:

- Months = (Date of screening - Date of symptom onset/diagnosis)/12

For partial symptom onset/diagnosis date, if only the day is missing, then impute the day as the first day of the month; if both the day and month are missing, then impute it as 01 January of the year.

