9 COMPUTER SOFTWARE

All analyses will be performed by Chiltern using SAS® Version 9.3 or later. All summary tables and data listings will be prepared utilizing SAS® software.

The standard operating procedures (SOPs) of Chiltern will be followed in the creation and quality control of all data displays and analyses.

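### SAP 8.6 divides a date difference by 12 to get months of disease duration; in days, the most plausible unit, the results are 2.54 times too large

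*SAP*

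**What the plan says.** SAP Section 8.6 (Disease History) plans descriptive statistics in the Safety Population for two variables, "Number of months since symptom onset" and "Number of months since diagnosis". For subjects whose dates are available, both are derived as "Months = (Date of screening - Date of symptom onset/diagnosis)/12". Partial dates are completed first: "if only the day is missing, then impute the day as the first day of the month", and if the month is missing too, 1 January of the year is used.

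Neither Section 8.6 nor any other part of the SAP or protocol states the unit of the date difference or gives another conversion. Section 9 says of the output: "All summary tables and data listings will be prepared utilizing SAS® software". Section 7.1 adds: "Subject listings of all data from the eCRF as well as any derived variables will be presented". Protocol Section 7.1.1 allows onset and diagnosis to be recorded either as a date or as a number of months.

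**The concern.** Twelve converts between years and months. It does not convert a difference between two calendar dates into months unless that difference is already in a unit for which 12 is the right divisor, and no ordinary unit qualifies.

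If the line is programmed as written, both disease-duration summaries and the derived values in the listings would be wrong. A short duration would not look wrong: 30.4 months in place of 12 is believable in a dementia cohort, so a plausibility check could pass it. Disease duration is one of the few descriptors of this group of up to 25 subjects, and the sample-size sections of both documents expect the results to support the planning of later studies.

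**Working it through.** The plan states no numerical result here, so there is no figure to reproduce. The check is of units.

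**Inputs**
- Formula: date difference divided by 12 (SAP 8.6), unit not stated.
- Target unit: months (SAP 8.6).
- Average month: 365.25/12 = 30.4375 days. This is a calendar constant that the documents do not give; a 30-day month is tried as the alternative.

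**Does any unit make 12 the right divisor?**

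| Unit of the difference | Correct conversion to months | Effect of dividing by 12 |
|---|---|---|
| Days | divide by 30.4375 | 30.4375/12 = 2.54 times too large |
| Weeks | divide by 30.4375/7 = 4.348 | 12/4.348 = 2.76 times too small |
| Months | none needed | 12 times too small (the result is in years) |
| Years | multiply by 12 | 12 × 12 = 144 times too small |

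No row returns months. The unit settles only the size and direction of the error.

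**Which unit is most plausible?** The formula subtracts the dates themselves, and in SAS the difference of two dates is a count of days. Where the SAP wants a coarser unit it says so: in Section 6.3, age is "the difference of the year of his/her informed consent date and the year of his/her birth". Section 8.6 has no such wording. The completion of partial dates to a calendar day fits a difference in days but does not prove it, since a full date is also needed to store the value as a date variable or to count calendar months.

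**Size if the difference is in days**

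| True months | Days (months × 30.4375) | SAP formula (days/12) | Excess |
|---|---|---|---|
| 12 | 365.25 | 30.4 | 18.4 |
| 36 | 1095.75 | 91.3 | 55.3 |
| 60 | 1826.25 | 152.2 | 92.2 |

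With 30-day months the factor is 30/12 = 2.50, so the choice of month length hardly matters.

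**Example with the SAP's own imputation rule (dates assumed).** Onset is known only as 2013 and becomes 1 January 2013; screening is on 1 January 2018.
- Difference: 5 × 365 + 1 leap day = 1826 days.
- SAP formula: 1826/12 = 152.2.
- Correct: 1826/30.4375 = 60.0 months.

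**Mixed recording.** The formula applies only where dates exist. Suppose a fraction p of subjects have dates, the rest have months recorded directly and used as they stand, and true durations are similar in both groups. The mean is then inflated by 1 + 1.54p: 2.54 at p = 1, and 1.77 at p = 0.5. In a mixed column no single constant corrects the published mean, SD or quartiles.

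**The case against.** The strongest objection is that the factor of 2.54 rests on a unit the SAP never states. Weeks, months or years would make the values too small, so even the direction depends on an assumption. This is right as far as it goes, and the factor should be read as conditional on days. It does not rescue the formula, which fails in every row of the unit table.

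A second objection is that completing partial dates to a day says nothing about the unit. That stands. The case for days rests on plain subtraction of dates in SAS, supported by the contrast with the wording for age. The SAP names the software but not the programming step.

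Third, the factor applies only to durations derived from dates. Subjects recorded directly in months are unaffected, and the case report form, which would show how many there are, is not among the documents. This also stands.

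Fourth, Section 9 commits to quality control under standard operating procedures, and a figure such as 152 months for a five-year history might well be noticed. It might. But the SAP is the specification that such a check works from, and a silent correction would depart from it and leave the choice of conversion to the programmer.

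Finally, the effect is only descriptive. Section 7.8 says "No subgroup analysis will be performed", Section 7.2 has no covariate adjustment for the primary analyses, and the imaging and safety analyses do not use these durations. This limits the importance of the error but does not remove it, because the study's planned output is descriptive throughout.

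**Conclusion.** The formula is wrong as written: dividing by 12 does not give months from a date difference in days, weeks, months or years. In days, durations derived from dates are 2.54 times too large (2.50 with 30-day months). That factor assumes plain subtraction of dates in SAS, and it applies to the whole summary only if every duration comes from dates.

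The consequence is limited to two baseline descriptors and their listings. Imaging results, safety results and sample size are untouched, and the dates listed under Section 7.1 would allow the values to be recalculated. It should be corrected before the tables are programmed, but it does not threaten the study's conclusions.

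**What to change.** In SAP Section 8.6, replace the formula with: Months = (date of screening − date of symptom onset or diagnosis, in days) / 30.4375. State the unit explicitly.

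If the case report form holds only a number of months for some subjects, add a sentence saying that those values are used directly.

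The cost is one formula line and, if needed, one sentence. Nothing changes for patients, data collection or any other analysis.

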8.7 Medical/Surgical History and Concurrent Disease

Medical/Surgical History and Concurrent Disease will be presented in a listing for the safety population.

8.8 Concomitant Medications

A concomitant medication is defined as any medication given to the subject starting on or after the date of the screening visit or the medication started prior to the date of the screening visit but is reported as ongoing. A prior medication is any medication with a stop date prior to the date of screening visit.

If the start date of medication is unknown and the end date is known, then the medication will be considered:

- Prior to study medication if the end date is prior to the patient screening visit.
- Concomitant to study medication if the end date is either on the same day or after the screening visit or the end date is unknown.
- If both the start and end dates are unknown, then the medication will be considered as “concomitant medication”.

The medication will be summarized using frequency count and percentage for subjects in safety population by active ingredient within each ATC, with ATC and active ingredients sorted by descending frequency.

ATC classification level 4 will be used in summary tables and listings. If the ATC classification level 4 is missing then the ATC classification level 3 will be used. If the ATC classification level 3 is missing, then the ATC classification level 2 will be used. If the ATC classification level 2 is missing, then the ATC classification level 1 will be used.

All prior and concomitant medications will be presented in listing for the safety population.

8.9 Analysis of Efficacy Parameters

The Flortaucipir F 18 PET scan information and Flortaucipir F 18 PET results will be summarized using Efficacy Population. A subject listing will be presented.

8.9.1 Qualitative Assessment of Images

The visual read results will be categorized as Not consistent with AD pattern (τ AD-), and AD pattern (τ AD) (τ AD+, τ AD++) for Flortaucipir F 18 PET results. The visual read results will be summarized by frequency count and percentage for the analysis populations (ITT and per protocol)

8.9.2 Quantitative Assessment of Images

The MUBADA SUVR for Flortaucipir F 18 results will be summarized using descriptive statistics for analysis populations (ITT or per protocol). This analysis will be repeated for the following brain regions: temporal, parietal and caudate, and frontal.

8.9.3 Other Efficacy Variables

8.9.3.1 Increased Neocortical Activity by Brain Regions

Increased neocortical Flortaucipir F 18 activity by hemisphere and region, calculated as regional SUV_r values will be presented in a listing.

8.10 Analysis of Safety

All safety data will be summarized using the Safety Population.

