7.1.1.1. Screening Florbetapir F 18 PET scan

The screening florbetapir F 18 PET scan is to be performed to assess for evidence of amyloid pathology and should be interpreted by the local reader prior to enrollment. Amyloid scans that have been obtained within 3 years of screening can be submitted for review by the local reader for enrollment criteria. If deemed interpretable, the subject would not need to complete the screening florbetapir F 18 PET scan.

- For women of childbearing potential, a negative pregnancy test must be obtained within 24 hours prior to injection; If screening serum pregnancy test obtained within 24 hours prior to injection, the pregnancy test need not be repeated.
- Height and body weight will be measured prior to injection.
- A physician or licensed/credentialed medical professional (that is, a PET technologist, imaging center nurse, or a regional equivalent) designated by the site principal investigator must see the subject prior to administration of Florbetapir F 18 Injection to determine if they are still suitable to undergo the scan;
- Vital signs will be taken (pulse rate, respiratory rate, supine blood pressure) immediately prior to injection of florbetapir F 18;
- Subjects will receive a single IV bolus injection of approximately 370 MBq (10 mCi) +10% of florbetapir F 18 followed by a saline flush. A 20-minute continuous, dynamic PET brain scan will begin approximately 50 minutes following the dose administration;
- A physician or licensed/credentialed medical professional (that is, a PET technologist, imaging center nurse, or a regional equivalent) designated by

Protocol ¹⁸F-AV-1451-A19: “¹⁸F-AV-1451 PET Imaging in Subjects with Frontotemporal Dementia”

the site principal investigator will see the subject prior to discharge from the imaging center to evaluate the subject’s readiness for discharge;

- A follow-up phone call to the subject, or designated decision maker, will be conducted between 2 or 3 business days of the imaging day, but not before 48 hours post-injection, to confirm subject well-being and to collect information about any new adverse events. If both of these days are not business days, the follow-up phone call can occur the following business day.

7.1.2. **¹⁸F-AV-1451 PET Imaging Visit: Visit 2**

The ¹⁸F-AV-1451 PET scan should be performed at least 16 hours apart from the Florbetapir F 18 PET scan due to the half-life of fluorine 18. The following assessments will be performed for all subjects:

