Pre-existing conditions (i.e., undesirable experiences, signs or symptoms that begin prior to the Screening Visit) will be recorded on the medical history eCRF pages. During the study, site personnel will record any change in the condition(s) and occurrence and nature of any AEs. Signs and symptoms that are believed to be due to the pre-existing condition(s) (started prior to dose of study medication) do not have to be recorded in the AEs section of the eCRF, unless there is an increasing in frequency and severity. Additionally, signs or symptoms or changes in pre-existing conditions that occur outside the trial defined adverse event reporting period (e.g., between each imaging visit will be recorded in medical history).

An adverse event is any untoward medical occurrence associated with the use of a drug in humans, whether or not considered drug related. For the purposes of this study, untoward medical occurrences will be considered associated with the use of ¹⁸F-AV-1451, and thus be reported as adverse events, if they occur within 48 hours after administration of ¹⁸F-AV-1451. Untoward medical occurrences will be considered associated with the use of Florbetapir F 18 injection, if they occur within 48 hours after Florbetapir F 18 injection administration. Adverse events associated with the use of ¹⁸F-AV-1451 or Florbetapir F 18 injection will be recorded as treatment emergent relative to the respective drug. Adverse experiences that occur after administration of either drug but outside the 48 hour reporting window will not be reported unless the investigator believes they are attributable to the drug.

Trial-emergent adverse events are undesirable experiences, signs or symptoms that begin, or worsen in intensity or frequency, after the informed consent, and

Protocol ¹⁸F-AV-1451-A19: “¹⁸F-AV-1451 PET Imaging in Subjects with Frontotemporal Dementia”

prior to administration of study drug at the imaging visit. In order to capture possible adverse effects of trial participation, trial-emergent AEs will also be reported during the baseline imaging period but not during the 48 hour windows following the administration of ¹⁸F-AV-1451 or Florbetapir. These will be recorded on the adverse event pages.

The end of study, for the purpose of adverse event reporting, is defined as 48 hours after the last study drug administration.

Serious Adverse Event (SAE)

A SAE is an AE that results in one of the following outcomes or constitutes one of the following events:

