8.1.2. Populations for Analysis

The efficacy population will include all patients for whom image data are available. All analyses involving tau imaging outcomes will be based on the efficacy population. Safety population will include all patients that received at least one dose of ¹⁸F-AV-1451 compound or Florbetapir F 18. Safety evaluation will be based on safety population.

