8.2.2. Safety Analyses

Adverse events including injection site reactions will be summarized in terms of number and percentage of patients experiencing an AE. The AEs will be summarized by system organ class (SOC) and preferred term using Medical Dictionary for Regulatory Activities (MedDRA) terms. Adverse events will also be presented by severity, relationship to treatment, and seriousness. All patients who experience SAEs, or who discontinue due to AEs, will be summarized.

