8 STATISTICAL ANALYSIS

8.1 Analysis Populations

The study will use following analysis populations for data summarization. Frequency count and percentage of subjects in each analysis population will be summarized.

Population	Definition	Displays
Enrolled Population	The Enrolled Population will consist of all subjects who signed informed consent and have data captured in the clinical database.	Disposition information will be summarized using the Enrolled Population.
Safety Population	The Safety Population will include all subjects who received at least one dose of Flortaucipir F 18 or Florbetapir F 18 injection.	All demographic, baseline and safety endpoints will be using the Safety Population.
ITT Population	The ITT Population will include all subjects in safety population, for whom image data are available i.e. who have a valid Flortaucipir F 18 scan assessment [SUV _r (quantitative) and/or visual reads (qualitative)].	All analyses involving imaging outcomes will be based on the ITT Population.
Per Protocol Population	The Per Protocol Population will include all subjects in ITT population who were classified on Florbetapir positive ($\alpha\beta+$) by either investigator or Avid.	All analyses involving imaging outcomes will be based on the Per Protocol Population.

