8.10.2 Adverse Events

All AE summary tables will include only TEAEs, unless otherwise specified.

Adverse events will be summarized by SOC and PT. A subject will only be counted once per SOC and PT.

For AEs by severity grade (mild, moderate, severe), if a subject has multiple events occurring in the same SOC or same PT, then the event with the maximum intensity (i.e. severe) will be counted.

For AEs by relationship to study drug and protocol procedure will be summarized as Related vs. Not Related. If a subject has multiple events occurring in the same SOC or same PT, the event associated with the study drug will be summarized.

AEs will be summarized by descending frequency, then alphabetically by SOC and preferred term.

An overall summary of AEs will be presented and will include:

- Subjects with any Trial Emergent AEs
- Subjects with at least one TEAE
- Subjects with any severe or moderate TEAE
- Subjects with any TEAE related to Florbetapir F 18
- Subjects with any TEAE related to Flortaucipir F 18
- Subjects with any TEAE related to protocol procedure
- Subjects with any serious TEAE
- Subjects with any TEAE resulting in death
- Subjects with any TEAE leading to study discontinuation

The following summary tables will be presented by SOC and PT:

- Trial Emergent AEs
- All TEAEs
- TEAEs by PT
- TEAEs by severity
- TEAEs by relationship to Florbetapir F 18
- TEAEs by relationship to ¹⁸F-AV-1451
- TEAEs by relationship to protocol procedure
- Serious TEAEs
- TEAEs resulting in death
- TEAEs leading to study discontinuation

The following listings will be presented by subject:

- All AEs
- Serious TEAEs
- TEAEs leading to study discontinuation
- TEAEs resulting in deaths

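### The florbetapir- and flortaucipir-specific adverse-event percentages are taken over a population that can include subjects never given that tracer on study

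*SAP*

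**What the plan says.** SAP 8.1 defines one safety set: "The Safety Population will include all subjects who received at least one dose of Flortaucipir F 18 or Florbetapir F 18 injection". Protocol 8.1.2 has the same rule for ¹⁸F-AV-1451 (flortaucipir) and florbetapir: "Safety population will include all patients that received at least one dose of ¹⁸F-AV-1451 compound or Florbetapir F 18". SAP 8.10 then places every safety summary on that set: "All safety data will be summarized using the Safety Population". Under Protocol 8.2.2, AEs are "summarized in terms of number and percentage of patients experiencing an AE".

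SAP 8.10.2 nonetheless plans tracer-specific output. The overall summary has the row "Subjects with any TEAE related to Flortaucipir F 18" and a matching row for florbetapir, and there is an SOC/PT table of TEAEs by relationship to each tracer. SAP 6.6.2.1 treats an event as related to a tracer when it occurs within 48 hours of that tracer's injection. Protocol 7.7.2 also works by tracer: events associated with either drug "will be recorded as treatment emergent relative to the respective drug".

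The design does not give both tracers to everyone. Exclusion criterion 8 (Protocol 5.3.2) removes subjects with a positive florbetapir scan, which is known only after florbetapir has been injected. In the other direction, an amyloid scan from the previous 3 years can replace the on-study scan: "If deemed interpretable, the subject would not need to complete the screening florbetapir F 18 PET scan" (Protocol 7.1.1.1; the SAP repeats this in 4.1).

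**The concern.** The numerator and denominator of the tracer-specific percentages describe different groups. Leaving aside the worst-case rule for a missing relationship, only a subject dosed with a tracer can contribute an event related to it. The denominator also holds subjects who received only the other tracer, and no section of the SAP sets a by-tracer denominator. The error runs one way: each unexposed subject lowers the reported percentage.

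The sole secondary objective is to enlarge the flortaucipir safety database. The percentage with a flortaucipir-related event is a natural summary for that purpose, and it falls as more subjects stop between the two injections, whatever the tracer does.

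**Working it through.** **No stated figure to reproduce.** The planned size, up to 25 subjects (Protocol 8.1.1, SAP 4.5), is a descriptive choice. The documents give no expected AE rate and no number of single-tracer subjects. The counts below are therefore assumptions.

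**Who is in the Safety Population.** Let *b* be the subjects given both tracers, *s* those given florbetapir only (amyloid-positive or withdrawn), and *m* those given flortaucipir only (prior scan accepted). All three groups meet the SAP 8.1 definition. Nothing there removes screen failures, and SAP 7.3 keeps the available data of subjects who discontinue. Hence

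- Safety N = *b* + *s* + *m*
- flortaucipir-dosed n = *b* + *m*
- florbetapir-dosed n = *b* + *s*
- reported % = events / Safety N; exposed % = events / n dosed; ratio of the two = n dosed / Safety N

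**Flortaucipir, 25 subjects dosed, no prior scans (*m* = 0).** If a fraction *x* of florbetapir-dosed subjects does not proceed, Safety N = 25/(1 − *x*). One event among the 25 exposed is 1/25 = 4.0%.

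| *x* (assumed) | Safety N | Reported | Exposed | Ratio |
|---|---|---|---|---|
| 0% | 25 | 1/25 = 4.0% | 4.0% | 1.00 |
| 10% | 27.8, about 28 | 1/28 = 3.6% | 4.0% | 0.89 |
| 20% | 31.25, about 31 | 1/31 = 3.2% | 4.0% | 0.81 |
| 40% | 41.7, about 42 | 1/42 = 2.4% | 4.0% | 0.60 |

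The 40% is illustrative. It borrows the figure in Protocol section 1 for AD pathology at autopsy among dementia patients given a non-AD diagnosis. It is not an expected florbetapir-positivity rate.

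**If the florbetapir-only subjects fall within a total of 25.** SAP 8.1 counts everyone consented with data as enrolled, whereas Protocol 7.1.1.1 puts the scan reading before enrollment, so this reading is also open. With *s* = 2, 5 or 10, one flortaucipir event is reported as 1/25 = 4.0% where the exposed figure is 1/23 = 4.3%, 1/20 = 5.0% or 1/15 = 6.7%.

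**Florbetapir, 25 in the Safety Population, all given flortaucipir, 12 using a prior scan.** Florbetapir-dosed n = 25 − 12 = 13. One event is reported as 1/25 = 4.0%; the exposed figure is 1/13 = 7.7% (ratio 13/25 = 0.52).

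**Both at once.** Take 25 given flortaucipir, 10 of them on a prior scan, and 20% of on-study florbetapir subjects not proceeding. Then *b* = 15, *s* = 15 × 0.2/0.8 = 3.75, about 4, and Safety N = 29. One event is reported as 1/29 = 3.4% for either tracer, against 1/25 = 4.0% for flortaucipir and 1/19 = 5.3% for florbetapir.

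**The case against.** The study is a small descriptive Phase I with no inferential analysis (SAP 7.6). Its secondary objective is to add to a safety database, not to estimate a rate. Counts appear beside percentages and are correct. The exposure summary in SAP 8.10.1 should show how many received each tracer, and the AE and exposure listings allow a by-tracer reading. The either-tracer population comes from the protocol, so the SAP did not introduce it. All of this stands and limits the weight of the point. It does not make the planned percentages correct: a summary table should not have to be repaired from listings.

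Four stronger readings are tempting, and the documents do not support them.

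- A reader might infer that the pooled rows are wrong. They are valid as rates after any study tracer.
- A reader might infer that the severity and serious tables leave flortaucipir unreadable. They do not separate the tracers, but the by-subject listings do, and relatedness by 48-hour window already makes the relationship tables close to tracer-specific.
- A reader might infer that upper confidence limits for AE risk will be misreported. SAP 7.1 plans counts and percentages only, so no table would carry such a limit.
- A reader might take "All values will be summarized as a single group" (SAP 7.1) as a decision to pool the tracers. The sentence goes on to name the diagnostic group, frontotemporal dementia, and says nothing about tracers.

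**Conclusion.** As written, the tracer-specific TEAE percentages are understated whenever some Safety subjects did not receive that tracer on study and at least one related event occurs. The conclusion follows from the definitions. The size does not, because the number of single-tracer subjects is not given. Over the assumed ranges the reported percentage is between 0.52 and 1.00 of the exposed one. It is unchanged for a tracer that every Safety subject receives. The primary imaging results are untouched. This is a should-fix: it bears on the secondary objective but distorts no count and no pooled row.

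**What to change.** In SAP 8.1, define two subsets of the Safety Population: Flortaucipir-dosed and Florbetapir-dosed (on study). In SAP 8.10.2:

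- use the number dosed with the tracer as the denominator for its overall-summary row and its SOC/PT relationship table, and print each n;
- show the severity and serious TEAE tables by tracer as well, in line with the protocol's drug-specific treatment emergence, and keep the either-tracer total;
- state an allocation rule. The two scans may be as little as 16 hours apart (Protocol 7.1.2), so the 48-hour windows can overlap. Count an event that falls in both windows under both tracers and once in the total;
- place a later event that the investigator attributes to a drug under that tracer, and say that it enters these tables, since the TEAE definition in SAP 6.6.2 ends at 48 hours.

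The cost is SAP wording and a few extra table columns. No new data are needed. The reported percentages become somewhat less favourable, by an amount that depends on how many subjects received only one tracer.
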